17.1 Adverse Events

AEs will be coded using the MedDRA Version 21.0 or higher.

An AE will be considered as 'treatment emergent' if it occurred after the first IMP administration of each period or if it was present prior to first IMP administration but exacerbated after the first IMP administration of each period. All other adverse events will be considered 'pre-treatment'.

In the case where it is not possible to define an AE as TEAE or not, the AE will be classified as TEAE as the most conservative approach.

The AE listings will include the following items:

- System organ class
- Preferred term
- Investigator's description
- Whether the event is treatment-emergent
- Trial treatment at onset of event
- Date and time of onset and resolution
- Duration of the event
- Date and time of last administration before AE
- Study Day
- Severity
- Causality relationship to investigational product
- Outcome
- Action taken to investigational product
- Other action

- Seriousness

17.1.1 All Adverse Events

A summary table describing all the TEAEs occurring during the trial will be produced overall and by group as well as by treatment for each group using frequency of events and number and percentage of subjects experiencing these events overall and by SOC and PT.

Group/SOC terms will be sorted by decreasing total frequency. Preferred terms (PT) within each group/SOC term will likewise be sorted by decreasing total frequency.

In addition, all TEAEs will be tabulated by severity and relationship to IMP in the same manner.

The relationship to the trial treatment, as indicated by the investigator, is classified as ‘unrelated’ or ‘related’. TEAE with a related or missing relationship to the trial treatment will be regarded as ‘related’.

Multiple occurrences of the same TEAE in one subject during the same treatment in the trial will be counted as multiple events in the frequency counts for adverse events. If a subject experiences more than one occurrence of the same AE during the same treatment in the trial, the subject will only be counted once for that treatment using the worst severity and the strongest relationship. The AE will be categorized as ‘unrelated’ only when all relationship records are ‘unrelated’, otherwise it will be classed as ‘related’ in the corresponding relationship summaries.

In case a subject had events with missing and non-missing severities, the maximum of the non-missing severities will be displayed. In case all the TEAEs of a subject are all with missing severities then Moderate will be used unless there is any evidence that it should be Severe.

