Appendix 4 Adverse Events: Definitions and Procedures for Recording, Evaluating, Follow-up, and Reporting

Definitions

Adverse Event

An AE is any untoward medical occurrence in a participant administered a pharmaceutical product, regardless of causal relationship with this treatment. Therefore, an AE can be any unfavorable and unintended sign (including an abnormal laboratory finding), symptom, or disease temporally associated with the use of a medicinal product, regardless if it is considered related to the medicinal product.

For surgical or diagnostic procedures, the condition/illness leading to such a procedure is considered as the AE rather than the procedure itself.

The Investigator is required to grade the severity or toxicity of each AE.

Investigators must assess the severity of AEs per the Qualitative Toxicity Scale, as follows:

Mild: The participant is aware of the event or symptom, but the event or symptom is easily tolerated.

Moderate: The participant experiences sufficient discomfort to interfere with or reduce his or her usual level of activity.

Severe: Significant impairment of functioning: the participant is unable to carry out his or her usual activities.

Investigators must also systematically assess the causal relationship of AEs to the IMP using the following definitions. Decisive factors for the assessment of causal relationship of an AE to the IMP include, but may not be limited to, temporal relationship between the AE and the IMP, known side effects of IMP, medical history, concomitant medication, course of the underlying disease, and study procedures.

Unrelated: Not reasonably related to the IMP. AE could not medically (pharmacologically/clinically) be attributed to the IMP under study in this clinical study protocol. A reasonable alternative explanation must be available.

Related: Reasonably related to the IMP. AE could medically (pharmacologically/clinically) be attributed to the IMP under study in this clinical study protocol.

Adverse Drug Reaction

In accordance with GCP, ADR is an adverse event considered related to drug treatment.

Abnormal Laboratory Findings and Other Abnormal Investigational Findings

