The Rsq should be ≥ 0.800 and the observation period over which the regression line is estimated should be at least two-fold the resulting $t_{1/2}$ itself. If these criteria are not met, then the rate constants and all derived parameters (e.g., $\text{AUC}_{0 \rightarrow \infty}$, $\text{AUC}_{\text{extra}\%}$, CL/f , $t_{1/2}$, and $\text{V}_{\text{z/f}}$) will be included in the parameter outputs and descriptive statistics but will be flagged and discussed appropriately. Any flags should be included in the study specific SDTM.

To ensure a reliable estimate of the extent of exposure in pivotal trials (e.g., BE), $\text{AUC}_{\text{extra}\%}$ should be less than or equal to 20.0%. If $\text{AUC}_{\text{extra}\%}$ is greater than 20.0%, all parameters derived using λ_z (i.e., $\text{AUC}_{0 \rightarrow \infty}$, $\text{AUC}_{\text{extra}\%}$, λ_z , $t_{1/2}$, $\text{V}_{\text{z/f}}$, and CL/f) will not be included in the calculation of descriptive statistics or statistical analyses.

The dose amount for IMP administered is that of the active, free drug substance only, and is synonymous with the measured analyte. No adjustment for the dose amount value of IMP will be applied when 'dose' is used in calculating PK parameters with formulas needing a dose value.

The Phoenix WinNonlin NCA Core Output will be provided in a separate listing.

17 Safety Evaluation

The subsections in this section include specifications for summarizing safety endpoints that are common across clinical trials such as adverse events, laboratory tests, ECG recordings and vital signs. Safety analyses will be done on the Safety Population. All safety data will be listed in individual subject listings by group, treatment sequence and subject.

All safety variables will be analyzed using descriptive statistics. For the evaluation of safety parameters, the continuous variables will be summarized descriptively by N, mean, median, SD, Q1-Q3, and minimum and maximum values.

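### SAP 17.1.1: the two rules for missing TEAE severity are inconsistent, so adding a Mild event can lower the severity shown for a subject

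*SAP*

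**What the plan says.** SAP 17.1.1 plans severity tables for TEAEs: "In addition, all TEAEs will be tabulated by severity and relationship to IMP in the same manner". The main TEAE table to which this refers is produced overall, by food group and by treatment within group, with event counts and subject counts by SOC and PT.

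For repeated occurrences of the same event during the same treatment, the counting rule is: "the subject will only be counted once for that treatment using the worst severity and the strongest relationship".

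Two sentences at the end of the section then deal with missing grades:

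- Some grades known: "In case a subject had events with missing and non-missing severities, the maximum of the non-missing severities will be displayed".
- No grade known, where the closing exception is for evidence pointing to the Severe grade: "In case all the TEAEs of a subject are all with missing severities then Moderate will be used unless there is any evidence that it".

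For missing causality, the same section takes a different route: "TEAE with a related or missing relationship to the trial treatment will be regarded as ‘related". The worse category is assigned first and the strongest relationship is taken afterwards.

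The severity scale in Protocol Appendix 4 has three ordered levels: Mild, Moderate and Severe. The protocol gives no rule for a missing grade. Protocol 9.4.1 excludes imputation unless otherwise stated, so the SAP sentences stand alone.

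**The concern.** A worst-severity summary should not improve when a subject reports more events. Under these two sentences it can. An ungraded event counts as Moderate while it stands alone, and counts for nothing once a Mild event appears beside it. The SAP's own default for an unknown grade is therefore dropped in the one mixed case where it would matter without further evidence.

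The rule also departs from the approach elsewhere in the SAP. Missing causality is imputed before the strongest value is taken. In SAP 17.1, an event that cannot be classified as treatment-emergent or not is classified as treatment-emergent, on the stated ground of conservatism. No reason is given for treating severity differently.

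A second gap is the level of application. The counting rule is tied to the same event during the same treatment. The missing-severity sentences speak only of a subject's events. In a crossover each participant receives both products, so the level decides which grades can bear on which product's column.

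What is at stake is the accuracy of the severity tables that serve the secondary safety and tolerability objective.

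**Working it through.** The SAP states no figure here to reproduce. The check applies its two sentences as a rule and asks whether the displayed grade can ever fall when an event is added.

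**Inputs**
- Scale: Mild = 1, Moderate = 2, Severe = 3 (Protocol Appendix 4), with missing as a separate state.
- Rule as written (SAP 17.1.1): if any grade is known, display the maximum of the known grades. If none is known, display 2, or 3 where there is evidence of Severe.
- Alternative: replace each missing grade by 2, or by 3 where there is evidence of Severe, then display the maximum.
- Planned group sizes: 38 fasting, 16 fed (SAP 7.2).

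**Results for the key combinations**

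| Grades present | As written, no evidence of Severe | As written, evidence of Severe | Impute first, no evidence | Impute first, evidence |
|---|---|---|---|---|
| missing | Moderate | Severe | Moderate | Severe |
| missing, Mild | Mild | Mild | Moderate | Severe |
| missing, Moderate | Moderate | Moderate | Moderate | Severe |
| missing, Severe | Severe | Severe | Severe | Severe |
| missing, missing, Mild | Mild | Mild | Moderate | Severe |

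**Enumeration.** With four states, the unordered sets of one, two or three events number 4 + 10 + 20 = 34. Adding one further event of each state gives 34 × 4 = 136 cases.

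- As written, no evidence of Severe: the grade falls in 3 of 136 cases. In each, a Mild event joins a set in which every grade is missing (Moderate to Mild).
- As written, evidence of Severe: the grade falls in 6 of 136 cases. Three go from Severe to Mild (two grades) and three from Severe to Moderate (one grade).
- Impute first: 0 of 136, with or without evidence.

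These counts describe the logic of the rule. They are not probabilities of occurrence.

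The evidence clause does not repair the rule. It sits only in the all-missing sentence, so a single known grade switches it off. That is why the drop can reach two grades.

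**Level of application.** Take, as an illustration, one ungraded event on the test product and one Mild event of a different term on the reference product.
- Applied within preferred term and treatment, the ungraded event stands alone and is shown as Moderate.
- Applied across all of the subject's events, the subject has both missing and known grades, and the Mild grade governs.

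The inconsistency does not depend on this choice. Two occurrences of the same term on the same product, one ungraded and one Mild, give Mild on either reading.

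**Size of one case.** 1/16 = 6.3% of the planned fed group; 1/38 = 2.6% of the planned fasting group.

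**The case against.** The case on the other side has several parts, and much of it stands.

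- **Missing grades should be rare.** The protocol says: "The Investigator is required to grade the severity or toxicity of each AE". Protocol 8.3.2 lists severity among the items that must be recorded for each event, and SAP Section 8 allows the final analysis only after all queries are resolved. The study is single-center, with participants inpatient from Day -1 to Day 10. This stands and limits the practical effect.
- **Little depends on the tables.** SAP Section 17 says: "All safety variables will be analyzed using descriptive statistics". Each event is listed individually with its severity and the treatment at onset (SAP 17.1), and imputed information is flagged in listings (SAP 11.14). This stands too.
- **The true grade is unknown.** Moderate is a default for use when nothing is known, and borrowing the observed grade of another occurrence of the same term can be defended. A reader might infer that the rule reports severity one grade below the truth. The documents do not support that: the shortfall is relative to the SAP's own default. What remains is that the SAP gives the same ungraded event two different values and does not say why.
- **Grades need not cross products.** A reader might infer that an ungraded event on one product takes its grade from a Mild event on the other. That follows only on the broader reading. The preceding paragraph counts per same event and same treatment, and the severity tables follow the layout of the main TEAE table, so the narrower reading is at least as natural. The supportable statement is that the level is not specified.
- **Several events do not in general lower the grade.** A known Severe grade never produces a fall, and a known Moderate grade does so only where there is evidence of Severe.

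**Conclusion.** The point holds as an internal inconsistency in a fallback rule. As written, an added Mild event can lower the displayed severity by one grade, or by two where there is evidence of Severe. It occurs only when the highest known grade is below the value that would be imputed. The level at which the rule applies is not stated.

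The importance is low. The effect is confined to descriptive severity tables, is zero if no grade is missing, and does not touch the bioequivalence conclusion. The documents give no rate of missing grades, so no expected number of affected participants can be derived. The figures of 6.3% and 2.6% are one participant over the planned group size, not estimates. The conclusion rests on reading the two sentences of SAP 17.1.1 as written, with nothing in the protocol overriding them.

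**What to change.** Replace the two sentences in SAP 17.1.1 with a rule in two steps:

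1. For each TEAE with no severity grade, impute Moderate, or Severe where there is evidence for it, and flag the value as imputed in the listings, as SAP 11.14 already requires.
2. Then take the maximum severity within participant, treatment and SOC/PT.

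This keeps the SAP's own default, applies the evidence clause to every ungraded event, and follows the same order as the causality rule. It settles the level of application, so no grade can pass between products. It also gives each ungraded event a grade for the event counts, which the present subject-level sentences do not supply.

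The cost is two sentences and one event-level derivation in the programming. No new data are needed. The trade-off is that some ungraded events will appear as Moderate beside Mild graded ones; the flag in the listings lets a reader see which.

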17.1.2 Adverse Events Leading to Treatment Discontinuation

AEs leading to permanent discontinuation of IMP will be identified as those records with a response of “Drug Withdrawn” to the item “Action taken with study drug” on the “Adverse Events Details” page of the eCRF.

For AEs leading to discontinuation of IMP, summaries of incidence rates (frequencies and percentages) by SOC and PT will be prepared.

All adverse events leading to trial or treatment discontinuation will be listed by group, treatment sequence and subject including SOC, PT and investigators’ verbatim.

17.2 Deaths, Other Serious Adverse Events, and Other Significant Adverse Events

17.2.1 Deaths

AEs leading to Death are those events which are recorded as “Fatal” to the item “Change in severity and outcome” on the “Adverse Events Details” page of the eCRF. AEs leading to deaths will be listed by group, treatment sequence and subject including SOC, PT and investigators’ verbatim, if applicable.

17.2.2 Serious Adverse Events

Serious adverse events (SAEs) are those events recorded as “Yes” to the item “Serious adverse event” on the “Adverse Events Details” page of the eCRF. All SAEs will be listed by group, treatment sequence and subject including SOC, PT and investigators’ verbatim.

17.3 Clinical Laboratory Evaluation

Results from the central laboratory will be included in the reporting of this study for hematology, biochemistry, and urinalysis. Laboratory evaluations to be included in the outputs are as below:

Hematology: Erythrocytes, Hemoglobin, Hematocrit, Mean corpuscular volume, Mean corpuscular hemoglobin, Mean corpuscular hemoglobin concentration, Red blood cell distribution width, Platelets, Mean platelet volume, Thrombocytocrit, Platelet distribution width, White blood cells, Neutrophils (both percentage and absolute counts), Monocytes (both percentage and absolute counts), Lymphocytes (both percentage and absolute counts).

Biochemistry: Alanine Aminotransferase (ALT), Aspartate Aminotransferase (AST), Total Bilirubin, Total Bilirubin, Direct Bilirubin, Indirect Bilirubin, Protein total, Albumin, Globulin, Albumin/globulin ratio, Alkaline Phosphatase, Glutamyl Transpeptidase, Urea Nitrogen, Creatinine, Cholesterol, Triglycerides, Glucose, Creatine Kinase, Creatine Phosphokinase MB Isoenzyme, Lactate Dehydrogenase, Calcium, Phosphorus, α -Amylase, Sodium, Potassium, Chloride.

Urinalysis: Appearance, Blood, Nitrite, Ketone, Protein, Glucose, Leukocytes, pH, Microscopic examination (Microscopic examination will be performed if dipstick test is positive for leukocytes, blood, nitrites, or proteins).

All hematology, biochemistry and urinalysis quantitative parameters will be summarized using descriptive statistics overall and by treatment sequence for each group at baseline and at end of study visit with raw data and change from baseline.

For all hematology and biochemistry parameters, frequency tables based on the classification of values as Low, Normal, High and Missing with respect to the reference ranges will be summarized by treatment sequence at baseline and end of study for each group. Frequency tables of urinalysis will be summarized by treatment sequence at baseline and end of study for each group, based on different types of classification rules. For urinalysis parameter, pH, the classification of values as Low, Normal, High and Missing will be applied. For urinalysis parameters, Blood, Nitrite, Ketone, Protein and Glucose, the classification of values as Normal/-, +-, +, ++, +++, +++++ will be applied. For urinalysis parameters, Appearance and Microscopic Examination, the classification of values

as Normal, Abnormal, Missing, or Total will be applied. For urinalysis parameters, Leukocytes, the classification of values as Not Negative, Negative, Missing and Total will be applied.

In addition, shift tables from baseline to end of study for all hematology, biochemistry and urinalysis will be summarized and presented by treatment sequence for each group at End of Study.

All marked abnormal laboratory values will be listed by subject, treatment sequence and group.

All data will be listed by group, treatment sequence, subject, treatment, visit, and time point.

17.4 Vital Signs

The following Vital Signs measurements will be reported for this study:

- Systolic Blood Pressure (mmHg)
- Diastolic Blood Pressure (mmHg)
- Pulse Rate (bpm)
- Temperature (°C)
- Respiratory Rate (breaths/min)

Systolic and diastolic blood pressures (mmHg) and pulse rate (beats/min) measurements as well as body temperature (°C) and respiration (breaths/min) will be presented by descriptive statistics overall and by treatment sequence for each group at baseline and end of study visit, and by group, treatment and time point for the values obtained during the treatment periods as raw data and change from baseline in the corresponding treatment period.

Frequency tables based on the classification of values as Low, Normal, High and Missing with respect to the reference ranges will be summarized by treatment sequence at end of study for each group, and by group, treatment and time point for the values obtained during the treatment period.

All marked abnormal for vital signs values will be listed.

All data will be listed by group, treatment sequence, subject, treatment, visit, and time point.

Markedly abnormal quantitative Vital Sign measurements will be identified in accordance with the following predefined markedly abnormal criteria:

Variable	Unit	Low	High
SBP	mmHg	< 85 mmHg	> 139 mmHg
DBP	mmHg	< 50 mmHg	> 90 mmHg

Variable	Unit	Low	High
Pulse rate	bpm	< 50 Beats/min	> 100 Beats/min
Body temperature	°C	< 36 °C	> 37.3 °C

17.5 Other Safety or Tolerability Evaluations

17.5.1 ECG Evaluation

Results from the 12-Led Electrocardiogram (ECG) be presented by descriptive statistics overall and by treatment sequence for each group at baseline and end of study visit.

The following ECG parameters will be reported for this study:

- RR Interval (ms)
- PR Interval (ms)
- QRS Duration (ms)
- QT Interval (ms)
- QTcB (Bazett) (ms)
- QTcF (Fridericia) (ms)
- Heart Rate (beats/min)
- Rhythm (sinusal – other).

Frequency tables for overall evaluation of ECG based on the classification of values as Normal, ANCS (Abnormal, Not Clinically Significant), ACS (Abnormal, Clinically Significant) and Missing will be presented by treatment sequence and overall for each group at the end of study visit.

12-lead ECG parameters and result of ECG will be listed in individual subject listing by group, treatment sequence, subject, visit, treatment and time point. All marked abnormal values of ECG evaluation will be listed by subject, treatment sequence and group.

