5.1 Inclusion Criteria

Participants are eligible to be included in the study only if all the following criteria apply:

1. Are 18 to 55 years of age inclusive, at the time of signing the informed consent.
2. Are overtly healthy as determined by medical evaluation, including medical history and a physical examination.
3. Have a body weight within 50 to 90 kg and BMI within the range 18 to 30 kg/m² (inclusive).
4. Are Chinese male and female (at least 1/4 of each gender per study group)
 - A male participant must agree to use and to have their female partners use a highly effective contraception (i.e., methods with a failure rate of less than 1 % per year) as detailed in [Appendix 3](#) of this protocol for a period of at least 1 month before and after dosing.
 - A female is eligible if she is not pregnant (i.e., after a confirmed menstrual period and a negative serum pregnancy test), not breastfeeding, and at least one of the following conditions applies:
 - a. Is **not** a woman of childbearing potential (WOCBP), as defined in [Appendix 3](#).

OR

5. Can give signed informed consent, as indicated in [Appendix 2](#) (Study Governance), which includes compliance with the requirements and restrictions listed in the informed consent form (ICF) and this protocol.
6. Non-smoker (0 cigarettes, pipes, cigars, or others) since at least 3 months.
7. All values for biochemistry and hematology tests of blood and urine within the normal range or showing no clinically relevant deviation as judged by the Investigator.
8. Electrocardiogram recording (12 lead ECG) without signs of clinically relevant pathology as judged by the Investigator.
9. Pulse, body temperature, and respiration in sitting position within the normal range or showing no clinically relevant deviation as judged by the Investigator. Blood pressure in sitting position within normal range: ≥ 90 mmHg and ≤ 139 mmHg for systolic blood pressure; ≥ 60 mmHg and ≤ 90 mmHg for diastolic blood pressure.

10. Negative screen for alcohol and drugs of abuse (cannabis, benzodiazepines, barbiturates, opiates, cocaine, and methyl amphetamine) at screening and on admission.
11. Negative screen for hepatitis A virus (HAV) antibodies, hepatitis B surface antigen (HBsAg), hepatitis C virus (HCV) antibodies, human immunodeficiency virus (HIV) antibodies, and *Treponema pallidum* (TP) antibodies.

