11.8 Definition of baseline

Unless otherwise specified, baseline for end of study is defined as the last non-missing measurement taken prior to or on the day of the first IMP administration (including unscheduled assessments as applicable). However, if time is missing, an unscheduled assessment on study day 1 will be considered to have been obtained after study treatment administration.

For vital signs, the assessment performed within 1 hour (± 30 minutes) prior to IMP administration in each treatment period will be considered as baseline for the treatment period. If there is no time point, the last non-missing assessment prior to dosing in each period will be taken as baseline.

In the case where the last non-missing measurement and the dosing date/time coincide, that measurement will be considered baseline, but medications commencing on the first IMP administration date will be considered post-baseline.

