13.3 Other Baseline Characteristics

The following baseline characteristics will be reported overall and by treatment sequence for each food consumption group:

- Nicotine and Alcohol Consumption
- Serology: HAV antibody, HBsAg, HCV antibody, HIV antibody, TP antibody

Baseline characteristics with respect to vital signs, ECG recordings and laboratory tests will be part of Section 17 (Safety Evaluation).

Results of chest x-ray and serum pregnancy test (for women of childbearing potential) will be presented only in the listings.

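### SAP 17.5.1 tabulates the overall ECG evaluation at end of study only, so the summary cannot separate pre-existing from new abnormalities that are not clinically significant (ANCS)

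*SAP*

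**What the plan says.** SAP 17.5.1 plans two ECG summaries with different time points.

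- ECG results are to "be presented by descriptive statistics overall and by treatment sequence for each group at baseline and end of study visit". The parameters then listed are RR, PR, QRS, QT, QTcB, QTcF, heart rate and rhythm.
- The overall evaluation (Normal, ANCS, ACS, Missing) gets frequency tables that "will be presented by treatment sequence and overall for each group at the end of study visit".

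The section also states that "12-lead ECG parameters and result of ECG will be listed in individual subject listing", sorted among other things by visit and time point. It mentions neither a shift table nor change from baseline.

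For laboratory data, SAP 17.3 does more. Descriptive statistics include change from baseline, frequency tables "will be summarized by treatment sequence at baseline and end of study for each group", and "shift tables from baseline to end of study for all hematology, biochemistry and urinalysis will be summarized".

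For entry, Protocol 5.1, criterion 8, requires "Electrocardiogram recording (12 lead ECG) without signs of clinically relevant pathology as judged by the Investigator". Protocol Table 1 schedules ECGs at screening, Day -1, Day 1, Day 8 and Day 10; footnote h places the Day 1 and Day 8 tracings 4 hours after dosing.

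SAP 11.8 defines the general baseline as "the last non-missing measurement taken prior to or on the day of the first IMP administration".

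**The concern.** Criterion 8 excludes tracings judged clinically relevant. It does not exclude tracings that are abnormal but judged not relevant, which is the ANCS category. A participant who enters with such a tracing and still has it on Day 10 is counted as ANCS in the end-of-study table, exactly as one whose tracing became abnormal on study. Anyone reading that table would want to know how many findings are new, and the table cannot say.

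The ECG intervals have a milder version of the same problem. Means at baseline and at end of study are planned, but the within-participant change is not.

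At stake is the clarity of one descriptive summary under the secondary safety objective. The data needed to do better are already collected before dosing.

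**Working it through.** The plan states no figure on this point, so there is nothing to reproduce. The check is a comparison of the texts, followed by what each table layout can show.

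**1. Side by side**

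| | Laboratory (17.3) | Vital signs (17.4) | ECG (17.5.1) |
|---|---|---|---|
| Descriptive statistics at baseline and end of study | Yes | Yes | Yes |
| Change from baseline | Yes | Yes, worded for the treatment periods | No |
| Frequency table at baseline | Yes | No | No |
| Frequency table at end of study | Yes | Yes | Yes (overall evaluation) |
| Shift table | Yes | No | No |

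Only 17.3 is a full precedent.

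**2. What each layout identifies**

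In a group of n participants with no missing tracings, let B be the number ANCS at baseline, E the number ANCS at end of study, and N the number ANCS at end of study but not at baseline.

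- Planned table: only E is shown, so N can be anything from 0 to E.
- Baseline column added: max(0, E − B) ≤ N ≤ min(E, n − B). Take hypothetical counts in the fed group: n = 16, B = 3, E = 3. The lower limit is max(0, 3 − 3) = 0 and the upper limit is min(3, 16 − 3) = 3. N is still undetermined.
- Shift table: N is read directly from the cells.

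A baseline column alone is therefore not enough.

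**3. Intervals and heart rate**

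If the same participants contribute at both visits, the mean change equals the difference of the two planned means. Its spread does not follow from them: SD(change)² = SD(B)² + SD(E)² − 2r·SD(B)·SD(E), and the within-participant correlation r is not reported. The largest individual change cannot be recovered either.

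**4. Possible size**

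Inputs: 38 fasting and 16 fed participants (SAP 7.2). The share p entering with an ANCS tracing that persists to Day 10 is an assumption. With no effect of drug, the expected end-of-study count is n × p.

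| p (assumed) | Fasting, n = 38 | Fed, n = 16 | Total, n = 54 |
|---|---|---|---|
| 0.05 | 1.9 | 0.8 | 2.7 |
| 0.10 | 3.8 | 1.6 | 5.4 |
| 0.20 | 7.6 | 3.2 | 10.8 |

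**5. Which tracing is baseline**

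The last pre-dose ECG in Table 1 is on Day -1. The only ECG scheduled on Day 1 is 4 hours postdose. Because SAP 11.8 admits a measurement on the day of first dosing, a literal reading makes that postdose tracing the last qualifying one. Other wording in 11.8 points to a pre-dose intention: an unscheduled Day 1 assessment with no time is treated as obtained after dosing. Table 1 also labels the screening columns as baseline. The intention is fairly clear, but the definition does not secure it.

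**The case against.** The strongest reply is that very little is lost.

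- **Baseline ECG is summarised.** The 17.5.1 parameters, including the categorical item rhythm, are presented at baseline. This meets the commitment in SAP 13.3 to cover baseline ECG in Section 17. A reader might infer that baseline ECG data go unused; the text does not support that. One could also stretch the descriptive-statistics sentence to cover the overall evaluation, but the sentence on the frequency tables names end of study alone.
- **The listing allows tracing.** With 54 participants, old and new ANCS findings can be separated by reading the by-visit listing. This stands, and it limits the point to the summary table.
- **Important changes are caught elsewhere.** Criterion 8 in effect excludes ACS at entry, so an ACS tracing at Day 10 would be read as new. Protocol Appendix 4 sends ECG findings that are symptomatic, lead to discontinuation or are otherwise medically important into adverse event reporting. Protocol 9.4.4 specifically names ECG listings with abnormal values flagged. All of this stands; what remains is ANCS.
- **Vital signs follow a similar pattern.** The 17.4 frequency table also lacks a baseline column. This stands, so the comparison should be with 17.3 only.
- **The table shells are not in the public documents.** SAP 11.1 says they set format and content, and they may include a baseline column. That is possible, but the SAP text should say so.

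Two stronger readings also fail. One is that chance differences between sequences in entry ANCS could mislead. By Day 10, completers of either sequence have received both products, so such a difference carries no product comparison. The other is that, with no untreated arm, the pre-dose tracing is the only reference. The crossover also provides a 4-hour ECG after each product in the same participant.

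**Conclusion.** The point holds in a limited form. As written, the only table of the overall ECG evaluation mixes pre-existing with new ANCS findings, and no change from baseline is planned for the intervals. It concerns ANCS, not ACS, and it concerns the summary, not the individual record. It has no bearing on the bioequivalence conclusion.

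It is a minor improvement to descriptive safety reporting. How many participants are involved is unknown. The illustrative counts rest on an assumed entry share of 5% to 20% and on every such tracing persisting to Day 10, and they are not an estimate for this trial. The conclusion itself does not depend on that rate: no value above zero makes the planned table informative about new findings.

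**What to change.** In SAP 17.5.1:

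1. Replace the end-of-study-only table with a shift table of Normal, ANCS, ACS and Missing from baseline to end of study, by treatment sequence and overall within each food group, following the laboratory shift tables in 17.3.
2. Add change from baseline to end of study for RR, PR, QRS, QT, QTcB, QTcF and heart rate.
3. Define ECG baseline, in 17.5.1 or as an exception in 11.8, as the last ECG recorded before the first dose in Period 1, so that the 4-hour Day 1 tracing cannot qualify.

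The cost is SAP wording and one table layout, with the shells brought into line. No new data or visits are needed, since the tracings at screening, Day -1 and Day 10 are already scheduled.
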